3.2 Treatment Phase

During the Treatment Phase, patients will be followed according to the assessments schedule in Table 8-3, and Table 8-4. Objective tumor response will be assessed at W16 \pm 1, W24 \pm 1 and then every 12 \pm 1 weeks from the randomization date, according to RECIST 1.1 criteria (central + local assessment up to first progression, then only local assessment).

Duration of the Treatment Phase:

• Before the PFS primary analysis:

The Treatment Phase is not fixed and the patients who are randomized should continue to receive the study treatments until progression or death (patients randomized in the Lutathera arm, will continue octreotide long-acting 30 mg injections after the completion of the 4 Lutathera treatments until progression or death; patients randomized in the octreotide long-acting arm will continue octreotide long-acting 60 mg injections until progression or death).

• After the PFS primary analysis:

The Treatment Phase becomes fixed and will stop at week 72 (patients randomized in the Lutathera arm, will continue octreotide long-acting 30 mg injections after the completion of the 4 Lutathera treatments until week 72 or earlier in case of progression or death; patients randomized in the octreotide long-acting arm will continue octreotide long-acting 60 mg injections until week 72 or earlier in case of progression or death).

In other words, before the PFS primary analysis (i.e. 99 evaluable and centrally confirmed disease progressions or death events), patients continue the Treatment Phase until progression; after the PFS primary analysis, the Treatment Phase duration is limited to 72 weeks.

At any time during the study (before or after the PFS primary analysis) any progressive patient (based on central imaging assessment) immediately ceases the Treatment Phase and proceeds to the Follow-up Phase (Table 8-3 and Table 8-4). If a patient discontinues Lutathera before centrally confirmed disease progression, the patient should be followed with tumor assessments as per initial CT/MRI schedule until centrally confirmed disease progression.

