The re-treatment phase will last until locally confirmed disease progression or until EoS, whichever occurs first. If a patient discontinues Lutathera before locally confirmed disease progression in re-treatment, the patient should be followed with tumor assessments as per initial CT/MRI schedule until locally confirmed disease progression. After re-treatment phase is complete, patients will be followed up for 3 years or until EoS, whichever occurs first (and at least 6 months after the last re-treatment dose in the study).

The time window to start re-treatment in this study is within 4 years after the last patient randomized.

For patients in Lutathera arm who are eligible for re-treatment beyond this window, Lutathera access for re-treatment may be granted via Post Study Drug Supply (PSDS) programs, based on local regulation (see Section 9.2.1).

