3.5 Follow up Phase

At the end of the Treatment Phase (or the optional Treatment Extension Phase in case of crossover, or the optional Re-treatment Phase) or after discontinuation for any cause (including disease progression), all patients will continue to be followed up at least every 6 months and up to 3 years (or until EoS, whatever comes first) to continue data collection for the secondary endpoints of the study, such as long term safety and overall survival.

During the Follow-up Phase, SAEs and adverse events of special interest (AESI) other than secondary hematological malignancies, related to the study treatment and AESI of secondary hematological malignancies irrespective of causality, will be reported. Anti-tumor treatments administered after progression/discontinuation, disease status based on local CT/MRI assessment, and OS data will be collected every 6 months (\pm 1 month) in both arms (see schedule of assessments in Table 8-3, and Table 8-4).

4 Rationale

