6.5.2.1 Dose modifying toxicities (DMTs) for Lutathera

For patients who do not tolerate the protocol-specified dosing schedule, dose adjustments are permitted to allow the patient to continue the study treatment.

The criteria for dose modifications of Lutathera for toxicities are outlined in Table 6-4.

If a patient requires a dose delay of > 16 consecutive weeks of Lutathera from the day of the previous dose, then the patient should be discontinued from the study treatment. In exceptional situations, if the patient is clearly benefiting from the study treatment (i.e. stable disease, partial response, complete response), and in the opinion of the investigator no safety concerns are present, after discussion with AAA Medical Monitor, the patient may remain on the study treatment.

For each patient, a maximum of one dose reduction will be allowed after which the patient will be discontinued from the study.

These dose changes must be recorded on the appropriate electronic case report form (eCRF).

Adverse Reaction	Worst Toxicity CTCAE Grade	Dose Modification
	(unless otherwise specified)	
Thrombocytopenia	First occurrence of: Grade 2 (PLT < 75 - 50 x $10^9/L$)	Withhold dose until complete or partial resolution (Grade 0 to 1).
	Grade 3 (PLT < 50 - 25 x 10 ⁹ /L) Grade 4 (PLT < 25 x 10 ⁹ /L)	If AE resolves before next planned Lutathera dose (i.e. within 9 weeks after the previous dose), administer next full dose of Lutathera (7.4 GBq / 200 mCi).
		If AE resolves within 9 – 16 weeks after the previous dose, resume Lutathera at 3.7 GBq (100 mCi). If reduced dose does not result in Grade 2, 3 or 4 thrombocytopenia, administer Lutathera at 7.4 GBq (200 mCi) for next dose.
		If AE does not resolve within 16 weeks after the previous dose, permanently discontinue Lutathera.
	Recurrent Grade 2, 3 or 4	Permanently discontinue Lutathera.
Anemia	First occurrence of:	Withhold dose until complete or partial resolution (Grade 0, 1, or 2).
	Grade 3 (Hgb < 8.0 g/dL);	If AE manaleurs hafens ment alaunad
	Grade 4 (life threatening	If AE resolves before next planned Lutathera dose (i.e. within 9 weeks
	consequences)	after the previous dose), administer next full dose of Lutathera (7.4 GBq / 200 mCi).

Table 6-4. Dose Modifications of Lutathera for Adverse Events

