	Recurrent Grade 3 or 4	If AE resolves within 9 – 16 weeks after the previous dose, resume Lutathera at 3.7 GBq (100 mCi). If reduced dose does not result in Grade 3 or 4 anemia, administer Lutathera at 7.4 GBq (200 mCi) for next dose. If AE does not resolve within 16 weeks after the previous dose, permanently discontinue Lutathera. Permanently discontinue Lutathera.
Neutropenia	First occurrence of:	Withhold dose until complete or
	Grade 3 (ANC < 1.0 - 0.5 x 10 ⁹ /L) Grade 4 (ANC < 0.5 x 10 ⁹ /L)	If AE resolves before next planned Lutathera dose (i.e. within 9 weeks after the previous dose), administer next full dose of Lutathera (7.4 GBq / 200 mCi). If AE resolves within 9 – 16 weeks after the previous dose, resume Lutathera at 3.7 GBq (100 mCi). If reduced dose does not result in Grade 3 or 4 neutropenia, administer Lutathera at 7.4 GBq (200 mCi) for next dose. If AE does not resolve within 16 weeks after the previous dose, permanently discontinue Lutathera.
	Recurrent Grade 3 or 4	Permanently discontinue Lutathera.
Renal Toxicity	 First occurrence of: Creatinine clearance less than 40 mL/min; calculated using Cockcroft Gault formula with actual body weight, or 40% increase from baseline serum creatinine, or 40% decrease from baseline creatinine clearance; calculated using Cockcroft Gault formula with actual body weight. 	Withhold dose until complete resolution. If AE resolves before next planned Lutathera dose (i.e. within 9 weeks after the previous dose), administer next full dose of Lutathera (7.4 GBq / 200 mCi). If AE resolves within 9 – 16 weeks after the previous dose, resume Lutathera at 3.7 GBq (100 mCi). If reduced dose does not result in renal toxicity, administer Lutathera at 7.4 GBq (200 mCi) as next dose.

		If AE does not resolve within 16 weeks after the previous dose, permanently discontinue Lutathera.
	Recurrent renal toxicity Grade 3 or 4	Permanently discontinue Lutathera.
Hepatotoxicity	First occurrence of: Bilirubinemia greater than 3 times the upper limit of normal (Grade 3 or 4), or	Withhold dose until complete or partial resolution (Grade 0, 1 or 2). If AE resolves before next planned Lutathera dose (i.e. within 9 weeks after the previous dose), administer next full dose of Lutathera (7.4 GBq / 200 mCi).
		If AE resolves within 9 – 16 weeks after the previous dose, resume Lutathera at 3.7 GBq (100 mCi). If reduced Lutathera dose does not result in G3 or 4 bilirubinemia, administer Lutathera at 7.4 GBq (200 mCi) as next dose.

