After resolution of a DMT, a patient may receive subsequent planned treatment(s) at the full dose (if resolved within 9 weeks after the previous dose), or at 50% of the standard treatment dose (if resolved within 9 - 16 weeks after the previous dose), if this is felt to be safe for the patient, or the risk-benefit assessment is favourable. If the same DMT reoccurs after treatment with the reduced Lutathera dose, the patient will remain in the study and continue the scheduled clinical / tumor assessments until tumor progression, but no further Lutathera treatment will be given. Octreotide long-acting 30 mg will be continued at monthly intervals. If the DMT event does not reoccur, the next treatment is at full dose, if it is considered to be safe for the patient, or the risk-benefit assessment is favourable.

If a patient experiences a DMT during Lutathera therapy, subsequent treatments with Lutathera are permissible, provided the DMT resolves within 16 weeks following the non-tolerated administration. In any case, the patient will continue the administration of 30 mg octreotide long-acting.

Lutathera overdose, has a very low probability of occurring since it will be supplied as a single dose "ready to use product" in order to avoid any manipulation outside the production facilities. In addition, the infusion system methods do not allow the concurrent use of two separate Lutathera solution vials (see pharmacy manual). No doubling of the administered radioactivity is ever allowed either in absolute amount or by shortening the time intervals between treatments. Treatments (amount of radioactivity and time of administration) will be monitored during the study and any unallowed treatment modification will be considered a major protocol violation.

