6.5.2.2 Dose modifying toxicities (DMTs) for Octreotide LAR

Control arm (Octreotide LAR 60 mg)

In the treatment arm with octreotide long-acting, a dose adjustment will be applied in case of Grade 3 or 4 toxicity, especially in presence of severe abdominal symptoms, and hypoglycaemia/ hyperglycemia possibly related to octreotide long-acting. The dose adjustment will also be applied if such adverse events are observed which are unlikely related to the study drug, but to other possible or concomitant causes, and the full administration of octreotide long-acting would represent a safety risk for the patient.

If a patient experiences a DMT during octreotide long-acting treatment, the subsequent treatment dose will be reduced from 60 mg to the previous well-tolerated dose (or even temporarily suspended) and then at the next treatment, the dose will be increased to the initial 60 mg dose of octreotide long-acting, if this is felt to be safe for the patient, or the risk-benefit assessment is favorable.

In any case (also in case of octreotide long-acting treatment dose suspension), the patient remains in the study and continues the scheduled clinical / tumor assessments until tumor progression, unless the patient's withdrawal becomes inevitable (Section 9 -Study discontinuation).

Lutathera arm (Octreotide LAR 30 mg)

All DMT recommendations in the control arm (Octreotide LAR 60 mg) are also applicable to the Lutathera arm, where Octreotide LAR is administered at the standard approved dosage (30 mg). Overall, the exact dose reduction levels, duration of suspension and criteria for re-increase and continuation of dose in the control arm will be defined by the treating physician based on clinical judgment and product leaflet.

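### Protocol 6.5.2.1 takes a patient off the study at the limit of one Lutathera dose reduction; this is probably a slip, and it contradicts the rules that stop Lutathera only

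*Protocol*

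**What the plan says.** Section 6.5.2.1 of the protocol sets the limit for each patient: "a maximum of one dose reduction will be allowed after which the patient will be discontinued from the study". The paragraph just before it, on dose delays beyond 16 weeks, uses a different object: "then the patient should be discontinued from the study treatment". Table 6-4, in the same section, stops Lutathera, and nothing else, when a toxicity recurs.

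The text after Table 6-4 then takes up recurrence at the reduced dose: "If the same DMT reoccurs after treatment with the reduced Lutathera dose, the patient will remain in the study". It goes on to say that assessments run to progression, Lutathera ends and octreotide 30 mg continues. Section 3.2 gives the imaging rule for anyone who stops Lutathera early in the initial phase: "the patient should be followed with tumor assessments as per initial CT/MRI schedule until centrally confirmed disease progression".

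In the SAP (1.3.1 and 2.5.3), stopping study treatment before a central PFS event is ignored under a treatment-policy strategy.

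**The concern.** The sentence is an operative instruction to sites. It sits in the section that a site would open when managing a toxicity. Followed literally, it would remove a patient from tumor assessment for a reason that is not progression, death or withdrawn consent. PFS would then be censored at the last adequate scan (SAP 2.5.4), although the estimand needs scans to continue after treatment stops.

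The effect would fall on one arm. Before cross-over, only the Lutathera arm can have a Lutathera dose reduction. The octreotide rule in 6.5.2.2, which governs the control arm and octreotide toxicity in the Lutathera arm, says that "the patient remains in the study and continues the scheduled clinical / tumor assessments until tumor progression". Patients in cross-over or re-treatment have already progressed, so for them the data at risk are mainly safety, PFS2 and survival.

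**Working it through.** **The plan's own figures.** With HR 0.50, one-sided 2.5%, 90% power and 2:1 allocation (Protocol 12.8.1), events = (1.960 + 1.282)² / [(2/9) × (ln 0.5)²] = 98.4, rounded up to 99. The critical HR is exp(−1.960 / √(99 × 2/9)) = 0.658. Both match the plan, and neither depends on the disputed sentence.

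**The texts side by side.**

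| Place | What stops | What continues |
|---|---|---|
| 6.5.2.1, disputed sentence | the study | nothing stated |
| 6.5.2.1, preceding paragraph | study treatment | nothing stated |
| Table 6-4, recurrent toxicity | Lutathera | nothing stated |
| 6.5.2.1, after Table 6-4 | Lutathera | assessments to progression; octreotide 30 mg |
| 6.1.1.1.3; Figure 6-1 footnote 4 | Lutathera | octreotide 30 mg every 4 weeks in the Treatment Phase |
| 3.2 | Lutathera | scans to central progression |
| 3.4 (re-treatment) | Lutathera | "the patient should be followed with tumor assessments as per initial CT/MRI schedule until locally confirmed disease progression" |
| 3.5 | any discontinuation | "all patients will continue to be followed up at least every 6 months and up to 3 years" |
| 6.5.3 | either drug | clinical and tumor assessments |
| 9.1.1; 9.2 | study treatment | participation unless consent is withdrawn; Follow up Phase |
| SAP 1.3.1, 2.5.3, 2.5.4 | study treatment | PFS follow-up; scans to documented progression |

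Only the first row removes the patient from the study.

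The sentence also fails on its own terms. It would act once a single reduction had been given, but Table 6-4 and the text after it return a patient who tolerates the reduced dose to full dose. The limit can only bite when a further reduction would be needed.

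Substituting study treatment for the study would not be the best repair. SAP 2.1.1.1 defines study treatment as the combination, and octreotide is meant to go on. The word needed is Lutathera.

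**Size if it were followed.** The documents give no dose-reduction rate, so only a per-patient figure is possible.

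- Inputs from Protocol 12.8.1: median PFS 30 months (Lutathera) and 15 months (control); 148 and 74 patients; accrual over 22.2 months; analysis at month 35.
- Assumptions: exponential PFS; uniform accrual; dropout of 15% by 24 months; removal between months 3 and 11, from the dosing intervals in Table 6-4.
- Rates: h = ln 2 / 30 = 0.0231 and d = −ln(0.85) / 24 = 0.00677 per month.
- Expected loss for a patient removed event-free at month m: the average, over follow-up t from 12.8 to 35 months, of [h/(h + d)] × [1 − exp(−(h + d)(t − m))].
- Result: 0.352 events at m = 3 and 0.238 at m = 11.
- Expected events by month 35 in the same model: 57.38 + 45.28 = 102.66.
- An arbitrary 10 patients removed would leave 102.66 − 3.52 = 99.14 to 102.66 − 2.38 = 100.28, still at least 99 by the planned date.

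**Who could still be affected.** Between the counts in the two amendment rationales (123 on 23 September 2021, 222 on 28 September 2022; 52.9 weeks), 222 − 123 = 99 patients were randomized. With a 24-week course and even accrual, 99 × 24/52.9 × 2/3 ≈ 30 of the 148 Lutathera patients were still in initial dosing at the second count. The SAP's last listed update, 22 August 2023, is about 47 weeks later, when a course on the regular schedule would be over.

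**The case against.** The strongest reply is that no careful site would act on this sentence. The right instruction appears later in the same section. Amendment 2.0 added the continued-scan rule to Sections 3.2 and 3.4. Section 9.1.1 says emphatically that stopping treatment is not withdrawal. Dosing by Table 6-4 already means setting the literal sentence aside. All of this stands, and it is why the point is small. It does not make the sentence correct.

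A reader might infer a real gap for a second, different toxicity, because the text after Table 6-4 speaks of the same toxicity recurring. The documents do not support that as a gap in follow-up. The next paragraph of 6.5.2.1, which covers any dose-modifying toxicity, continues octreotide 30 mg in every case. Section 6.1.1.1.3 and Figure 6-1 footnote 4 do the same when Lutathera is suspended or stopped for toxicity. Such a patient is still on study octreotide in the Treatment Phase. What remains is a dosing ambiguity: the first-occurrence rows of Table 6-4 run per toxicity and offer 3.7 GBq again, while the limit is per patient.

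A reader might also infer that all safety and survival data would be lost. That goes too far. Section 6.5.2 requires at least weekly follow-up of the toxicity until it resolves or stabilizes. Section 6.5.3 requires end-of-treatment exams even on early termination. Section 10.1.6 keeps SAE reporting open for 30 days after treatment. Section 9.1.1 lists survival status among the minimum data after treatment stops.

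**Conclusion.** The sentence is wrong as written, and the point is minor. That it is a slip is an inference, but a well-supported one, from the wording one paragraph earlier and the rule later in the same section.

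The harm depends on a site having followed this sentence against the others, and nothing in the documents shows that any did. Three stronger conclusions might be drawn, and none is supported:

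- That patients were lost, or will be.
- That the hazard ratio is biased in a known direction. The documents give neither the number of such patients nor their prognosis.
- That the analysis would slip past month 35. On the assumptions above, even 10 removals leave at least 99 expected events by then.

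What is left is a conditional, one-arm departure from the treatment-policy estimand. For primary PFS, little was left to protect by the SAP's last update. Lutathera dosing can still begin in cross-over or re-treatment up to 4 years after the last randomization, and there the correction protects safety, PFS2 and survival data.

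**What to change.** Replace the sentence in 6.5.2.1 with:

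> A maximum of one Lutathera dose reduction is allowed per patient, across all toxicities; if a further reduction would be needed, Lutathera is permanently discontinued. The patient remains in the study, continues octreotide long-acting 30 mg as specified for the phase (initial Treatment Phase: every 4 weeks), and continues tumor assessments (initial phase: until centrally confirmed progression; re-treatment: until locally confirmed progression; cross-over: local assessment) and safety and survival follow-up.

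The words on all toxicities also settle the dosing ambiguity in Table 6-4. The reference to the phase matters because octreotide is at the investigator's discretion in re-treatment (Section 3.4).

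The cost is one sentence. Section 14.1 requires a written amendment, and the change can wait for the next one. Until then, a short written clarification to sites pointing to Sections 3.2, 6.5.2.1 (the text after Table 6-4), 6.5.3 and 9.1.1 is enough, because those rules are already in the protocol. The 99 events, 222 patients and critical HR of 0.658 all stand.

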		If AE does not resolve within 16 weeks after the previous dose, permanently discontinue Lutathera.
	Defined as: Hypoalbuminemia less than 30 g/L with International Normalized Ratio (INR) >1.5.	 Withhold dose until complete or partial resolution (Grade 0 to 1). If AE resolves before next planned Lutathera dose (i.e. within 9 weeks after the previous dose), administer next full dose of Lutathera (7.4 GBq / 200 mCi). If AE resolves within 9 – 16 weeks after the previous dose, resume Lutathera at 3.7 GBq (100 mCi). If reduced Lutathera dose does not result in G2, 3 or 4 hypoalbuminemia, administer Lutathera at 7.4 GBq (200 mCi) as next dose. If AE does not resolve within 16 weeks after the previous dose, permanently discontinue Lutathera.
	Recurrent hepatotoxicity	Permanently discontinue Lutathera.
Any other CTCAE* Grade 3 or Grade 4 AE ¹	rirst occurrence of Grade 3 or 4	partial resolution (Grade 0 to 2).

		If AE resolves before next planned Lutathera dose (i.e. within 9 weeks after the previous dose), administer next full dose of Lutathera (7.4 GBq / 200 mCi).
		If AE resolves within 9 – 16 weeks after the previous dose, resume Lutathera at 3.7 GBq (100 mCi). If reduced dose does not result in Grade 3 or 4 toxicity, administer Lutathera at 7.4 GBq (200 mCi) as next dose.
		If AE does not resolve within 16 weeks after the previous dose, permanently discontinue Lutathera.
	Recurrent Grade 3 or 4	Permanently discontinue Lutathera.
Severe heart failure	NYHA class III or IV	Permanently discontinue Lutathera.
¹ No dose modification requir *CTCAE: Common Termino	red for hematological toxicities Grade 3 logy Criteria for Adverse Events, Natior	or Grade 4 solely due to lymphopenia nal Cancer Institute

In addition,

- permanently discontinue treatment with Lutathera if hypersensitivity due to the active substance or any of excipients of Lutathera is observed;
- Temporarily discontinue treatment with Lutathera, until resolution or stabilisation before treatment can be resumed.
 - Occurrence of an intercurrent disease (e.g. urinary tract infection);
 - Major surgery: wait 12 weeks after the date of surgery, then restart the treatment with Lutathera.

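### When a toxicity recurs after a full Lutathera dose, Table 6-4 requires permanent discontinuation, while the text below it in Section 6.5.2.1 can be read to permit further doses

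*Protocol*

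**What the plan says.** Protocol Section 6.5.2.1 opens by stating that "The criteria for dose modifications of Lutathera for toxicities are outlined in Table 6-4". The table separates first occurrence from recurrence, and its recurrence rows all lead to permanent discontinuation of Lutathera:

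- Thrombocytopenia: "Recurrent Grade 2, 3 or 4".
- Anemia, neutropenia and other adverse events: recurrence at Grade 3 or 4.
- Renal: "Recurrent renal toxicity Grade 3 or 4".
- Hepatic: "Recurrent hepatotoxicity", with no grade limit.

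None of these rows depends on whether the dose before the recurrence was full or reduced.

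The text below the table gives one rule for recurrence. It begins "If the same DMT reoccurs after treatment with the reduced Lutathera dose" and ends Lutathera while keeping the patient in the study. The next paragraph says that after a DMT "subsequent treatments with Lutathera are permissible, provided the DMT resolves within 16 weeks following the non-tolerated administration". That sentence carries no restriction to a first DMT.

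**The concern.** A site with a patient whose toxicity has come back after a full dose finds a prohibition in the table and, a page later, a general permission with a 16-week limit. Two sites could handle the same event differently, each citing Section 6.5.2.1.

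Three things are at stake. The first is patient safety, since this is a toxicity stopping rule. The second is consistency of exposure: the SAP (Section 2.4.1) summarizes number of doses, cumulative dose and dose modifications with reasons, and these would mix two practices. The third is how sites and patients are treated under other parts of the protocol. Section 6.5.2.1 counts any treatment modification that is not allowed as a major violation, so a site relying on the 16-week sentence could be cited under the table. Section 5.2.2 requires four initial Lutathera doses for re-treatment, so an early stop also closes that option.

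**Working it through.** The plan gives no figure to reproduce on this point. The check has three steps.

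**1. Can a recurrence follow a full dose under the protocol's own rules?** Yes, by two routes.

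- Route A: the first toxicity resolves quickly. The text says "a patient may receive subsequent planned treatment(s) at the full dose (if resolved within 9 weeks after the previous dose", and the first-occurrence rows of Table 6-4 agree.
- Route B: the first toxicity takes 9 to 16 weeks to resolve, a dose of 3.7 GBq is given and tolerated, and the next dose is full again. For neutropenia the table says: "If reduced dose does not result in Grade 3 or 4 neutropenia, administer Lutathera at 7.4 GBq (200 mCi) for next dose". The other toxicities have parallel wording.

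**2. What do the table and the text say in each case?** For the recurrences listed in the table:

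| Case | Table 6-4 | Text below the table |
|---|---|---|
| Recurrence after a reduced dose | Stop | Stop |
| Recurrence after a full dose, not resolved within 16 weeks | Stop | Further doses not permitted |
| Recurrence after a full dose, resolved within 16 weeks | Stop | No specific rule; the general sentence can be read to permit more |

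Only the third row conflicts, and the conflict is a prohibition against a permission. For renal toxicity it is narrower still. The first-occurrence criteria are based on creatinine, but the table's recurrence stop covers Grade 3 or 4 only.

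**3. How large can the difference in delivered dose be?** Inputs are the full dose of 7.4 GBq, four planned doses and the reduced dose of 3.7 GBq (Section 6.5.2.1 and Section 6.6).

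- Planned total: 4 × 7.4 = 29.6 GBq, as the protocol states.
- Route A, first event after dose 1, recurrence after a full dose 2. Stopping gives 2 × 7.4 = 14.8 GBq. Continuing with two full doses gives 29.6 GBq. The difference is 29.6 − 14.8 = 14.8 GBq, half the planned total.
- Same route, but the recurrence takes 9 to 16 weeks to resolve, so dose 3 is halved and, if tolerated, dose 4 is full: 3.7 + 7.4 = 11.1 GBq at most.
- Route B, first event after dose 1, reduced dose 2 tolerated, recurrence after a full dose 3. One dose remains, so the difference is at most 7.4 GBq.

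The documents give no rate of recurrence after a full dose, so the number of patients cannot be calculated.

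**The case against.** The strongest reply is that there is one rule, imperfectly repeated. The text never says that recurrence after a full dose is exempt; it is silent, and the table speaks. The 16-week sentence sets a necessary condition, an outer time limit, rather than a licence. Read as an unrestricted permission, it would also cancel the text's own stop after a reduced dose and the table's stop for severe heart failure, so it must already yield to specific stop rules. Section 9.1.1 makes discontinuation mandatory when the stopping criteria of Section 6.5.2 are met. The rationale for Amendment 1 says that discontinuation requirements were not changed.

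Much of this stands. A reader might infer that the text positively allows, or even requires, further doses after a recurrence on a full dose. The documents do not support that. The text addresses recurrence only in the reduced-dose case, the general sentence permits without obliging, and the preceding paragraph makes further dosing subject to safety or a favourable risk-benefit judgement. A site that stops complies with every sentence.

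What the reply does not supply is a written order of precedence. Section 6.5.2.1 says where the criteria are outlined, not that the table overrides the text. Section 9.1.1 points to the whole of Section 6.5.2, which contains both statements. The amendment rationale does not say which of them is the discontinuation requirement. Limiting the 16-week sentence to a first DMT is a sensible reading, but it is not written.

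A reader might also infer a threat to the primary result. That does not follow: SAP Sections 1.3.1 and 2.5.3 ignore discontinuation of study treatment for PFS (treatment policy), and Protocol Section 6.5.3 keeps patients who stop treatment in tumor assessment.

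**Conclusion.** The point holds in a narrow form. For a recurrence of the grades listed in Table 6-4, after a full dose and resolved within 16 weeks, the table forbids further Lutathera and the text can be read to permit it. No sentence says which prevails.

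The size is at most 14.8 of 29.6 GBq per patient. That ceiling belongs to one constructed scenario: first event after dose 1, recurrence after a full dose 2, and both remaining doses given in full. The documents do not show that any site has acted on the permissive reading.

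The consequence is for patient safety and the consistency of exposure data, not for the validity of the primary PFS test. Recruitment was complete by 28 September 2022 (Amendment 2.0 rationale), so the remaining relevance is to initial cycles still under way and to cross-over and re-treatment, which may start up to 4 years after the last randomization (Sections 3.3 and 3.4). This assumes that the same dose-modification rules are applied in those phases. The correction is worth making because it is specific and cheap and concerns a stopping rule.

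**What to change.** Reconcile Table 6-4 with the text below it. State one rule for the same toxicity recurring after a full dose, in the same words in both places, and say whether the 16-week sentence applies to first occurrences only. Which rule applies is for the sponsor and its clinical experts.

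The cost is a clarification letter or amendment wording and its communication to sites. No visits, assessments or analyses are added.
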